3.8.2 Vaccination status ascertainment

The exposure of interest in this study is a vaccination history with influenza vaccine or COVID-19 vaccine. The vaccination history includes date of administration, vaccine product and brand name, and the number of doses received (if applicable). Documenting the batch codes (where this is feasible) will allow identification of the vaccine brand, the vaccine content and the dose.

An individual is considered as vaccinated if they meet at least one of the following criteria:

- they are registered as vaccinated in a vaccination registry (preferred option);
 - they self-report having received an influenza or COVID-19 vaccination;
 - they are registered as vaccinated against influenza or COVID-19 in the GP information system;
 - their insurance company can show evidence of pharmacy delivery or re-imburement of influenza or COVID-19 vaccine/vaccination;
 - influenza or COVID-19 vaccination has been recorded in their vaccination card/vaccination booklet.
- *Each study site to document:*
- *the vaccine products used;*
 - *places of vaccination (GPs, specific vaccination centres, etc.);*
 - *the precise mode of vaccine ascertainment (self-report, card, registry, etc.);*
 - *if no precise dates of vaccination are collected, the variable allowing a patient to be defined as vaccinated or unvaccinated;*
 - *vaccine status ascertainment validation;*
 - *potential limitations of the vaccine status ascertainment.*

3.9 Data to be collected, including potential effect modifiers and confounding factors

3.9.1 Patient characteristics

Study sites can document the following patient characteristics to describe the study population:

- Age in years;
- Sex;
- GP code (in order to account for clustering by GP);
- Smoking history: never smoked, former smoker (stopped smoking for at least one year), current smoker (including stopped smoking less than one year ago). Smoking refers to any type of smoking (cigarettes, cigars, vaping, etc.);
- Pregnancy (yes/no).

⁵ The exact number of days will depend on the vaccine; this number may change and the protocol will be updated when more information is available.

3.9.2 Information on consultation

Type of consultation if different types of consultations are used: in practice, video, telephone, home, at a COVID-19 centre.

3.9.3 Clinical signs and symptoms

Collection of good quality symptom information is crucial for the VE study in order to be able to validate the case definition used (see section 3.5). As a minimum, if only CVE is estimated, data on the following symptoms should be collected:

- sudden onset;
- cough;
- fever;
- shortness of breath;
- coryza.

If IVE is estimated, the following **additional** variables should be collected to be able to determine which patients meet the EU ILI case definition:

- headache;
- sore throat;
- myalgia;
- malaise.

Study sites should collect the **date of symptom onset**.

➤ *Study sites to document the symptoms collected in their IVE and CVE studies.*

3.9.4 Information on swabbing and test results

For each patient, sites will collect information on:

- date of swabbing;
- place of swabbing (if relevant): GP practice, medical laboratory, COVID-19 centre, self-swabbing;
- type of influenza or COVID-19 test (PCR, rapid test);
- result of influenza or COVID-19 test.

Study sites carrying out testing for other respiratory viruses should also collect test results from any other respiratory viruses (e.g. rhinovirus, RSV, enterovirus, adenovirus, human metapneumovirus, seasonal coronaviruses, etc).

3.9.5 Pre-existing chronic conditions

If physicians are recruiting cases and controls using electronic medical records, the list of ICD codes can be used to document a study participant's chronic diseases (see Table 3):

The list below is comprehensive. A suggested minimum number of chronic diseases is specified below.

Table 3. ICD-10 codes for chronic diseases

Category	ICD-10
Anaemia	D50-D53, D55-64
Asplenia	Q89.0, Q20.6, Z90.8
Asthma	J45
Chronic liver disease	K70, K72-74, K75.4, K76.9
Cardiovascular diseases	A52.01, B37.6, B58.8, I05-9, I11, I13, I20-25, I26.0, I26.9, I27, I30-51, I97.0-1, R00.1, T81.7, T82.8, Q20-24, Q25.1-2, Q26.0-1, Q26.8, Q87.4, R01.1-2
Diabetes	E10-11
Hypertension	I10, I15.8, I15, I15.1, I15.2, I97, I27.0
Obesity	E66.01, E66.2, E66.9
Immunodeficiency* or organ transplant	B20, D80-84, D89.8-9, Z21, Z94
Neuromuscular disorders	G70.0, G70.2, G70.8, G70.9, G73.7
Renal disease	M10.3, N00-N08, N10-19, N20.0, N28.9
Dementia	F01, F03, F05, G30, G31, G91, G94
Stroke	G93, I67.8, I69
Rheumatologic diseases	M30-34, M35.0, M35.5, M35.8-9, M05-06, M08, M12.0
Cancer	C00-96
Lung disease excluding asthma)	A15, J40-44, J46-47, J60-J70, J80-86, J90-J94, J96, J99, J182, M34.8, M05.1
Tuberculosis	A15-A19

* Patients who are only treated with glucocorticoids and have no other immune deficiency, are considered immune suppressed when treated with high-dose corticosteroids (≥ 20 mg/day of prednisone or equivalent for ≥ 2 weeks) in the last three months.

If ICD codes are not available, a list of underlying conditions should be prepared by using a short questionnaire.

The list of underlying conditions in the questionnaire should include chronic conditions that are associated with an influenza (IVE) or COVID-19 (CVE) vaccination recommendation if possible:

- diabetes (study sites are encouraged to distinguish between type 1 and type 2);
- cardiovascular disease: myocardial infarction, angioplasty, coronary artery bypass surgery, stroke, transient ischemic attacks, treated hypercholesterolemia, not including hypertension;
- hypertension;
- chronic pulmonary disease (not including asthma);
- asthma;
- cancer;
- renal disease;
- chronic liver disease;
- rheumatologic diseases;
- obesity (see paragraph below);
- immunodeficiency⁶.

For obesity, if body mass index (BMI), or height and weight are not available, study sites can collect the following categories: BMI=30–39 and BMI \geq 40.

3.9.6 Vaccination status – vaccines other than influenza/COVID-19

If desired, study sites can collect information on vaccination against pneumococcal, RSV (once available) and/or other relevant vaccinations. In particular, RSV vaccination may be of relevance for IVE/CVE studies if recommended to similar target groups as influenza/COVID-19 and uptake is sufficiently high. Vaccination status variables could include:

- disease (pneumococcal/RSV/other);
- vaccination status;
- type of vaccine;

⁶ This can include active or recent treatment for solid tumour and hematologic malignancies; receipt of solid-organ or recent hematopoietic stem cell transplants; severe primary immunodeficiency; advanced or untreated HIV infection; active treatment with high-dose corticosteroids, alkylating agents, antimetabolites, tumour-necrosis (TNF) blockers, and other biologic agents that are immunosuppressive or immunomodulatory.

- number of doses;
- either date or year of vaccination;
- vaccination status ascertainment/source.

See section 3.8.2 on vaccination status ascertainment for information on methods for vaccination ascertainment (provided for COVID-19/influenza but applicable to other vaccines).

➤ *Each study site/country to document other vaccination status variables collected in their IVE and CVE studies.*

3.9.7 Antiviral administration

The use of antivirals should be documented: type, dosage (if possible) and date of administration (patients receiving antivirals in the two weeks prior to swabbing will be excluded from IVE analysis), as this may lead to misclassification biases.

➤ *Each study site/country to document antiviral variables collected in their IVE and CVE studies.*

3.9.8 Previous influenza or SARS-CoV-2 infection

If information on previous influenza infection within the current influenza season is known, this can be documented and controls with this infection will be excluded from IVE analyses.

Among those patients consulting their GP with COVID-19-like symptoms, some may have already had a SARS-CoV-2 infection in the past. People who have been previously infected may have a greater response to the vaccine or be less likely to be reinfected even if unvaccinated. If possible, study sites will collect the following information:

- whether the patient had a previous positive SARS-CoV-2 test(s) (yes/no/unknown);
- optional:
 - type(s) of test: PCR, rapid test, serology (in case of multiple positive test results, the most recent);
 - date(s) of test (in case of multiple positive test results, the most recent);
 - history of COVID-19, e.g. clinical confirmation.

In the primary analysis, controls testing SARS-CoV-2 positive in the previous 60 days will be excluded from the analysis. Sensitivity analyses will be carried out including controls who previously tested SARS-CoV-2 positive, and stratifying by previous SARS-CoV-2 infection, if sample size allows. Additionally, if sample size allows and information is available, controls previously infected with SARS-CoV-2 will be included or excluded depending on differing days since last infection, or variant of infection.

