3.7.3 Patient exclusion criteria

Patients are **excluded from the primary analysis** if they:

- refuse to participate in the study;
- are not swabbed;
- are unable to give informed consent or follow an interview in their native language because of aphasia, reduced consciousness, or other reasons;
- cannot be swabbed due to severe septum deviation, obstruction or other conditions that contra-indicate swabbing;
- have contraindications for the influenza (for IVE) or COVID-19 vaccination (for CVE);
- are institutionalised (virus exposure and risk factors may be different – specific cohort studies can be undertaken in these groups);
- are swabbed more than seven days (IVE) or 10 days (CVE) after symptom onset (to avoid false negatives; other numbers of days can be explored in sensitivity analyses);
- were vaccinated with a two-dose vaccine with fewer days between dose 1 and 2 than recommended by the manufacturer;
- had an inconclusive RT-PCR test.
- for IVE:
 - patients who had tested positive before to any influenza virus in the current season;
 - patients who had received antivirals 2 weeks prior to swabbing;

⁴ In certain circumstances, e.g. if COVID-19 testing centres are physician led, a consultation with a GP is not needed prior to the swab.

- for CVE:
 - patients who had tested previously positive to SARS-CoV-2 within 60 days prior to the current illness episode (other numbers of days and scenarios where date of previous test is unknown will be explored in sensitivity analyses);
 - controls positive to a seasonal coronavirus (e.g. HCoV-NL63, HCoV-229E, HCoV-OC43 and HCoV-HKU1) (as they may be affected by the vaccination).

Reasons for exclusion are documented.

Study sites can collect information on the exclusion factors and exclude patients according to available evidence on these factors.

In the main analysis, patients will be excluded if they were vaccinated with their most recent vaccine dose within 1–13 days preceding symptom onset (see section 3.8). In secondary analyses by time since vaccination, these patients could be included.

In sensitivity analyses, study sites can carry out the VE analyses with different cut-offs of numbers of days between onset and swabbing, using (for example) 5 and 7 days (see section 3.13.2).

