In further sensitivity analyses, patients reporting testing previously positive to SARS-CoV-2 will be included, and if sample size allows, an analysis stratified by previous infection will be carried out. Additionally, if sample size allows, patients testing previously positive to SARS-CoV-2 will be included or excluded with varying days since last infection, or variant of infection, if this information is available.

Please see section 3.13.2 on sensitivity analyses.

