rheum_dis		Numeric (categorical)	0 = No 1 = Yes 8 = Do not know	Rheumatological disease
Possible exclusion criteria				
antivir		Numeric (categorical)	0 = No 1 = Yes 8 = Do not know	Administration of antivirals prior to swabbing
res_home		Numeric (categorical)	0 = No 1 = Yes 8 = Do not know	Living in a residential home
contra		Numeric (categorical)	0 = No 1 = Yes 8 = Do not know	Contra-indication for COVID-19 or influenza vaccination
pretest_cov		Numeric (categorical)	0 = No 1 = Yes 8 = Do not know	Has the patient had any positive SARS-CoV-2 test prior to this illness episode?
Optional				
antivirdate		Date	dd/mm/yyyy	Date administration antiviral
antivirtype		Text		Type of antiviral (brand name)

Variable name	Collected by study site? (Please also indicate data source if not patient interview)	Type	Values and coding	Definition
prevtest_type_cov		Numeric (categorical)	1 = PCR 2 = Rapid test 3 = Serology 3 = Other (please specify) 8 = Do not know	Type of test used to detect a previous episode of SARS-CoV-2
prevtest_date_cov		Date	dd/mm/yyyy	Date of most recent positive SARS-CoV-2 test prior to this illness episode?
prevtest_flu		Numeric (categorical)	0 = No 1 = Yes 8 = Do not know	Has the patient had a positive influenza test in the current influenza season?
Other variables				
gpvisit		Numeric (count)	integer	Number of GP consultations in the previous 12 months
pregnant		Numeric (categorical)	0 = No 1 = Yes 8 = Do not know	Pregnancy status
Optional				
severity		Numeric (count)	integer	Number of hospitalisations in the previous 12 months for the chronic disease
smoking			0 = Never 1 = Former 2 = Current 9 = Do not know	Never, former (stopped smoking at least 1 year before inclusion in the study), current smoker (any smoking can be included: cigarettes, cigars, vaping, etc.)

1. If age in years not possible, please provide age in five-year age groups.

2. Anosmia and ageusia can also be combined into 'anosmia ageusia'.

3. Optional, but highly desirable.

4. Optional, but highly desirable.

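### Recent prior infection excludes all patients in section 3.7.3 but controls in section 3.9.8; a rule applied to controls alone makes eligibility depend on case status and can bias VE in either direction

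*Protocol*

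**What the plan says.** Section 3.7.3 lists who is "excluded from the primary analysis". For CVE the list includes "patients who had tested previously positive to SARS-CoV-2 within 60 days prior to the current illness episode"; for IVE it includes "patients who had tested positive before to any influenza virus in the current season". Both entries cover patients whatever their test result.

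Section 3.9.8 covers the same two situations but names controls. For COVID-19: "In the primary analysis, controls testing SARS-CoV-2 positive in the previous 60 days will be excluded from the analysis". For influenza: "controls with this infection will be excluded from IVE analyses".

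The sensitivity analyses split in the same way. The closing text of 3.7.3 reads "In further sensitivity analyses, patients reporting testing previously positive to SARS-CoV-2 will be included", and section 5.1.5 also asks for analyses that include any previously infected patients. Section 3.9.8 describes including, excluding and varying the window for controls.

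The 60 days also run back from differently worded points: the current illness episode in 3.7.3, and simply the previous 60 days in 3.9.8. No sentence gives either section precedence.

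**The concern.** A test-negative design compares vaccination odds between people who met the same entry conditions and differ only in the test result. An exclusion applied to test-negatives but not to test-positives breaks that. Under 3.7.3, a patient who tests positive today and also tested positive five weeks ago is out. Under 3.9.8 read literally, that patient stays in as a case, while a test-negative patient with the same history is removed. Some of those retained cases may still be positive from the earlier infection rather than newly infected.

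The composition of the primary analysis set is therefore defined in two ways, for both viruses. Sites may analyse their own data, so two sites could follow the same protocol and apply different filters.

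**Working it through.** **Texts side by side**

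| Item | 3.7.3 | 3.9.8 |
|---|---|---|
| CVE, primary analysis | patients | controls |
| IVE | patients | controls |
| CVE sensitivity analyses | patients (5.1.5 agrees) | controls |
| Start of the 60 days | current illness episode | not stated |

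The protocol gives no figure for the effect of this choice, so there is none to reproduce. VE = (1 − OR) × 100 is taken from section 3.13.1.

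**Model.** All inputs are assumptions. True OR is 0.6 (VE 40%) in people with and without a recent positive test. Coverage in controls without recent infection is 50%. A share p of controls, before any exclusion, is recently positive, with coverage c. Let s be the odds of recent positivity in cases divided by those odds in controls. Then s = 1 means cases and controls are recently positive equally often (in effect no protection from recent infection), s = 0.2 means one-fifth of the reinfection odds, and s = 0 means no repeat positives.

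1. Case coverage without recent infection: odds 0.6 × 1 = 0.6, so 0.6/1.6 = 0.375.
2. Case coverage with recent infection: odds 0.6 × c/(1 − c). For c = 0.35 the coverage is 0.2442; for c = 0.30 it is 0.2045.
3. Share q of cases recently positive: odds s × p/(1 − p).
4. Mixed case coverage: m = (1 − q) × 0.375 + q × (value from step 2).
5. With controls-only exclusion, control coverage is 50% (odds 1), so VE = 1 − m/(1 − m).

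Worked row, p = 10%, c = 30%, s = 1: q = 0.10; m = 0.9 × 0.375 + 0.1 × 0.2045 = 0.3580; odds 0.5575; VE 44.2%. With s = 0.2: q = 0.0217; m = 0.3713; odds 0.5906; VE 40.9%.

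| p | c | s = 0 | s = 0.1 | s = 0.2 | s = 1 |
|---|---|---|---|---|---|
| 5% | 35% | 40.0% | 40.2% | 40.3% | 41.7% |
| 10% | 30% | 40.0% | 40.5% | 40.9% | 44.2% |
| 15% | 30% | 40.0% | 40.8% | 41.5% | 46.3% |
| 10% | 50% | 40.0% | 40.0% | 40.0% | 40.0% |
| 10% | 60% | 40.0% | 39.7% | 39.4% | 37.4% |

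Excluding both groups removes the recently positive stratum and returns 40% in every row.

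**Second parametrisation as a check.** Let r1 and r0 be the recently positive shares in vaccinated and unvaccinated people, and let s now be the reinfection risk relative to people without recent infection. Controls-only exclusion gives OR × [1 + s·r1/(1 − r1)] / [1 + s·r0/(1 − r0)]. At OR 0.5 and r0 = 10%, for s = 0, 0.1, 0.5 and 1:

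- r1 = 5%: VE 50.0%, 50.3%, 51.4%, 52.6%
- r1 = 10%: VE 50.0% throughout
- r1 = 15%: VE 50.0%, 49.7%, 48.5%, 47.1%

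The conclusion on direction is the same: VE rises only if s > 0 and r1 < r0.

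**The case against.** The best defence is that 3.9.8 never says only controls and never says that such cases are kept. Section 3.7.3 is the dedicated exclusion section. Its closing text, 3.13.2 and 5.1.5 are not confined to controls, so a reader who applies both sections would exclude both groups. The pooled analysis is run by a central hub (3.13.3), which can apply one filter to everyone. This stands in part: 3.9.8 is the outlier, and the pooled estimate is better protected than site-level estimates. But 3.9.8 names controls repeatedly, for both viruses and for primary and sensitivity analyses, so it does not look like a single slip, and the hub also needs one rule.

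A reader might infer that the controls-only rule simply inflates VE. The documents do not support that. Section 5.1.5 says only that people who know of a past infection may be less likely to be vaccinated, gives one COVID-19 example and no figure, and says nothing about the 60-day window. It also calls lower control coverage a decrease for CVE but an increase for IVE, so it cannot settle the direction. Sections 3.9.8 and 5.1.5 both say previously infected people may be less likely to be reinfected, which pulls s towards zero and the bias with it. The s = 1 column is an upper-end case.

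A reader might also infer that the rules cannot be run because the test date is optional ("date(s) of test (in case of multiple positive test results, the most recent") and so is prevtest_flu. Section 3.7.3 provides for exclusion according to the evidence available and for sensitivity analyses where the date is unknown. Which fields are compulsory across varied surveillance systems is a feasibility choice. The repeated code in prevtest_type_cov ("3 = Serology 3 = Other (please specify") is a clerical slip in an optional variable and does not touch the 60-day rule.

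**Conclusion.** The contradiction is real. It concerns the primary CVE analysis explicitly, reaches IVE, and carries into the sensitivity analyses. It needs correcting whichever way the bias runs, because a test-negative study should not choose its participants by test result.

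The effect on VE is conditional. With the assumed lower coverage among recently positive people, the excess over a true 40% is about 0.3 to 1.5 points at one-fifth of the reinfection odds and 1.7 to 6.3 points with no protection. It is zero with no repeat positives or equal coverage. It becomes a shortfall of up to 2.6 points in the scenario with 10% recently positive and 60% coverage. The protocol supplies none of these inputs, so the figures show a range and do not predict the bias.

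**What to change.** In section 3.9.8, replace controls with patients (cases and controls) in three places: the influenza sentence, the 60-day primary rule, and the sentences on sensitivity analyses. This matches 3.7.3 and 5.1.5. Count the 60 days back from the current illness episode in both sections.

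The cost is a few sentences, plus the loss of those cases that a controls-only reading would have kept.

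Separately, and minor: give the Other category of prevtest_type_cov in Annex 1 its own unused code, and encourage sites to collect the previous-test date and prevtest_flu where feasible. That means two extra questions at sites that do not yet ask them.

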3.9.9 Previous tests used for the same illness episode

In order to better understand healthcare seeking behaviour and impact of home-testing, information on previous tests used for the current illness episode can be collected. This is applicable to the CVE study, as home tests are not routinely available for influenza.

This could be in form of the questions:

- Have you already done a test for SARS-CoV-2 for this illness episode?
- What type of test was it (PCR, rapid test)?
- What were the results (positive, negative, unknown)?

In the sensitivity analyses, patients testing positive at home for the current illness episode and negative in the study can be excluded from the analysis.

3.9.10 Healthcare utilisation in the previous 12 months

In order to document and control for healthcare seeking behaviour in the control groups and the severity of underlying conditions, study sites can collect:

- the number of GP visits made (face-to-face, or telephone consultations) in the past 12 months before inclusion in the study;
- the number of hospital admissions due to underlying conditions in the 12 months prior to inclusion in the study.

3.10 Sample size

The number of people included in the VE study will depend on the number of patients consulting at primary care level with ARI or ILI (depending on case definitions used) and the number of patients PCR-confirmed with influenza (IVE) or SARS-CoV-2 (CVE). Sample size will also depend on the duration of the period under study. The pooled analyses should not prevent study teams from including a big enough sample size to obtain reasonably precise estimates for each study site-specific analyses. Sample size estimation for VE studies differs from that for

hypothesis testing. We are more concerned with the precision of the VE estimate than with determining whether this estimate is significantly different from the null. For example, the confidence interval around a high VE estimate (e.g, 70%) may exclude 0% and provide little information (e.g. if the lower bound is equal to 1%). Better would be to aim for a more precise VE estimate (e.g. with a lower boundary of, say, 50%). Conversely, the confidence interval around a low VE estimate (e.g. 5–10%) may include 0% and still be informative. Besides, aiming for confidence intervals excluding 0% when the VE is low may result in unreasonably large sample sizes.

The following sample size estimates focus on the precision of the VE estimate (Table 4). As mathematically the lower confidence interval boundary is always larger than the upper confidence interval boundary, we focus on a precision of the lower confidence interval, ranging between 10 and 30%. We also assume a case to control ratio of 1:1. We include varying vaccine coverage among the source population between 30% and 90% (in 20% increments), varying vaccine effectiveness with the OR between 0.2 and 0.7 (equivalent to VE between 80% and 30%). The sample size for IVE and CVE may differ, as VE, vaccine coverage and positivity rates will vary. Sample size estimates should be estimated for IVE and for CVE and the higher estimates should be used.

A dynamic version of this table in Excel sheet format is available for study sites on request.

Table 4. Sample size calculations

Precision of lower CI boundary	Controls/case	Detectable OR	Vaccine coverage in source population/controls	Number of cases	Number of controls	VE	CI
0.3	1	0.2	0.3	85	85	80	51–92
0.3	1	0.3	0.3	118	118	70	40–85
0.3	1	0.4	0.3	157	157	60	30–77
0.3	1	0.5	0.3	203	203	50	20–69
0.3	1	0.6	0.3	255	255	40	10–60
0.3	1	0.7	0.3	314	314	30	0–51
0.2	1	0.2	0.3	148	148	80	60–90
0.2	1	0.3	0.3	216	216	70	50–82
0.2	1	0.4	0.3	299	299	60	40–73
0.2	1	0.5	0.3	395	395	50	30–64
0.2	1	0.6	0.3	507	507	40	20–55
0.2	1	0.7	0.3	633	633	30	10–46
0.1	1	0.2	0.3	433	433	80	70–87
0.1	1	0.3	0.3	681	681	70	60–77
0.1	1	0.4	0.3	985	985	60	50–68
0.1	1	0.5	0.3	1 346	1 346	50	40–58
0.1	1	0.6	0.3	1 764	1 764	40	30–49
0.1	1	0.7	0.3	2 240	2 240	30	20–39
0.3	1	0.1	0.5	32	32	90	60–98
0.3	1	0.2	0.5	51	51	80	51–92
0.3	1	0.3	0.5	77	77	70	40–85
0.3	1	0.4	0.5	109	109	60	30–77
0.3	1	0.5	0.5	148	148	50	20–69
0.3	1	0.6	0.5	193	193	40	10–60
0.3	1	0.7	0.5	246	246	30	0–51
0.2	1	0.2	0.5	90	90	80	60–90
0.2	1	0.3	0.5	142	142	70	50–82
0.2	1	0.4	0.5	208	208	60	40–73

Precision of lower CI boundary	Controls/case	Detectable OR	Vaccine coverage in source population/controls	Number of cases	Number of controls	VE	CI
0.2	1	0.5	0.5	289	289	50	30–64
0.2	1	0.6	0.5	384	384	40	20–55
0.2	1	0.7	0.5	495	495	30	10–46
0.1	1	0.2	0.5	262	262	80	70–87
0.1	1	0.3	0.5	447	447	70	60–78
0.1	1	0.4	0.5	687	687	60	50–68
0.1	1	0.5	0.5	983	983	50	40–58
0.1	1	0.6	0.5	1 337	1 337	40	30–49
0.1	1	0.7	0.5	1 751	1 751	30	20–39
0.3	1	0.2	0.7	43	43	80	50–92
0.3	1	0.3	0.7	71	71	70	40–85
0.3	1	0.4	0.7	108	108	60	30–77
0.3	1	0.5	0.7	153	153	50	20–69
0.3	1	0.6	0.7	207	207	40	10–60
0.3	1	0.7	0.7	272	272	30	0–51
0.2	1	0.2	0.7	75	75	80	60–90
0.2	1	0.3	0.7	131	131	70	50–82
0.2	1	0.4	0.7	205	205	60	40–73
0.2	1	0.5	0.7	298	298	50	30–64
0.2	1	0.6	0.7	412	412	40	20–55
0.2	1	0.7	0.7	548	548	30	10–46
0.1	1	0.2	0.7	219	219	80	70–87
0.1	1	0.3	0.7	413	413	70	60–78
0.1	1	0.4	0.7	676	676	60	50–68
0.1	1	0.5	0.7	1 015	1 015	50	40–58
0.1	1	0.6	0.7	1 435	1 435	40	30–49
0.1	1	0.7	0.7	1 941	1 941	30	20–39
0.3	1	0.2	0.9	71	71	80	50–92
0.3	1	0.3	0.9	129	129	70	40–85
0.3	1	0.4	0.9	208	208	60	30–77
0.3	1	0.5	0.9	310	310	50	20–69
0.3	1	0.6	0.9	437	437	40	10–60
0.3	1	0.7	0.9	591	591	30	0–51
0.2	1	0.2	0.9	124	124	0.8	60–90
0.2	1	0.3	0.9	238	238	0.7	50–82
0.2	1	0.4	0.9	397	397	0.6	40–73
0.2	1	0.5	0.9	605	605	0.5	30–64
0.2	1	0.6	0.9	868	868	0.4	20–55
0.2	1	0.7	0.9	1 190	1 190	0.3	10–46
0.1	1	0.2	0.9	361	361	0.8	70–87

Precision of lower CI boundary	Controls/case	Detectable OR	Vaccine coverage in source population/controls	Number of cases	Number of controls	VE	CI
0.1	1	0.3	0.9	751	751	0.7	60–78
0.1	1	0.4	0.9	1 311	1 311	0.6	50–68
0.1	1	0.5	0.9	2 061	2 061	0.5	40–58
0.1	1	0.6	0.9	3 022	3 022	0.4	30–49
0.1	1	0.7	0.9	4 216	4 216	0.3	20–39

CI: confidence interval; OR: odds ratio; VE: vaccine effectiveness.
Sample sizes calculated using Stata™'s power functionality.

The sample size estimates above are for the crude analysis and an adjusted analysis would require a higher sample size.

The sample size should also be respected for each population subgroup for which a sub (stratified) analysis is planned.

